### 9.6. Clinical Outcome Events

The following clinical outcome events will be captured in the study:

- Time from first dose to death (all cause)
- Time from first dose to liver-related death
- Time from first dose to liver transplant
- Time from first dose to MELD score  $\geq 15$  (for patients with MELD  $\leq 12$  at baseline)
- Time from first dose to earliest hospitalization for new onset or recurrence of:
  - variceal bleed
  - hepatic encephalopathy (as defined by a West Haven score of  $\geq 2$ )
  - spontaneous bacterial peritonitis (confirmed by diagnostic paracentesis)
- Time from first dose to uncontrolled ascites (diuretic resistant ascites requiring therapeutic paracentesis at a frequency of at least twice in a month)
- Time to first occurrence of any above listed clinical events

The incidence and time to first occurrence of any above listed clinical events will be summarized by treatment group using the log rank test stratified by the randomization stratification factor. The minimum and maximum time to clinical event will be presented. KM estimates of the

distribution of the time-to-event will be tabulated and graphed by treatment group. The tabulation will include the KM methodology using 25th, 50th (median), and 75th percentiles with associated 2-sided 95% CIs, as well as percentage of censored observations. The number and percent of patients censored and with events will be presented. The hazard ratio and 2-sided 95% CI will be estimated based on a Cox regression model stratified by randomization strata. The proportionality of hazards will be assessed using Schoenfeld residuals.

In addition, the incidence and time to each of the above clinical events, and the incidence and time to occurrence of HCC will be summarized by treatment group using the same methods as defined above.

For the time to event analyses, subjects who do not experience an event will be censored at the time of their last contact. Subjects with no data after randomization will be considered to have an event on Day 1 (first day of IP dosing). All time-to-event endpoints include only adjudicated events.

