### 10.3.1. Treatment-emergent Adverse Events

An AE is defined as a treatment emergent adverse event (TEAE) if it meets one or more of the following criteria:

- An AE starting on or after the first study drug dose and within 30 days after the last dose of study drug.

- An AE occurring prior to the first study drug dose that worsens (increase in grade) after the first study drug dose.

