### 10.3.5. Pruritus Adverse Events

Pruritus: Treatment-emergent pruritus, defined as any PT including “Prur” will be summarized separately by the treatment group, SOC, and PT as a subset of all TEAEs. This summary will be repeated for subjects with “new or worsened” pruritus events, as defined as follows:

- Mild, moderate, or severe treatment-emergent pruritus events in patients with no pruritus at baseline, or
- Worsening of the severity of the baseline condition in patients with pruritus at baseline.

Baseline pruritus is defined as the Investigator’s rating of severity as collected on the PBC Disease History eCRF. Patients whose baseline severity is severe will be counted as worsening if an AE of pruritus with severe is recorded.

An analysis of treatment-emergent pruritus event days per patient years on study will be performed. The days at each severity grade, including the total days of event, the total patient years on study, and the event days per patient year on study at each severity grade, including the total, will be summarized.

In order to explore the relationship between pruritus and the IP, the following time-to-event analyses will be performed:

- Time to first onset of treatment-emergent pruritus

The time to the start of the first episode = date of onset of first episode – date of first dose of IP + 1.

Patients who never reported an AE of pruritus will be censored at the date of last contact.

- Time to onset of the first moderate or severe treatment-emergent pruritus

The time to the start of the first moderate or severe pruritus = date of onset of the first moderate or severe pruritus – date of first dose of IP +1.

Patients who never reported a moderate or severe AE of pruritus will be censored at the date of completion or discontinuation.

- Time to onset of the first severe treatment-emergent pruritus

The time to the start of the first severe pruritus = date of onset of the first severe pruritus – date of first dose of IP +1.

Patients who never reported a severe AE of pruritus will be censored at the date of completion or discontinuation.

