The analysis of time to first onset of treatment-emergent pruritus AE, time to onset of the first moderate or severe treatment-emergent pruritus, and onset of the first severe treatment-emergent pruritus will include the number of patients with pruritus (first onset, first moderate or severe, first severe), the number of patients without pruritus (censored), and the minimum and maximum times in days. KM estimates will be calculated by treatment group. The tabulation will include the KM estimate methodology using 25th, 50th (median), and 75th percentiles of the medians and corresponding 2-sided 95% CIs, if the medians can be estimated as well as percentage of censored observations. KM estimates will be plotted as a “survival curve” for each treatment group.

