### **10.3.6. Fatigue Adverse Events**

Fatigue: Treatment-emergent fatigue is defined as any PT which includes “Fatigue.” New or worsened treatment-emergent fatigue is defined as follows:

- Any mild, moderate, or severe treatment-emergent fatigue events in patients with no fatigue at baseline, or
- Worsening of the severity of the baseline condition in patients with fatigue at baseline.

Baseline fatigue is defined as the Investigator’s rating of severity as collected on the PBC Disease History eCRF. Patients whose baseline severity is severe will be counted as worsening if an AE of fatigue with severe is recorded.

An analysis of treatment-emergent fatigue event days per patient years on study will be performed. The days at each severity grade, including the total days of event, the total patient

years on study, and the event days per patient year on study at each severity grade, including the total, will be summarized.

In order to explore the relationship between fatigue and the IP, the following time-to-event analyses will be performed:

- Time to first onset of treatment-emergent fatigue  
The time to the start of the first episode = date of onset of first episode – date of first dose of IP + 1.  
Patients who never reported an AE of fatigue will be censored at the date of last contact.
- Time to onset of the first moderate or severe treatment-emergent fatigue  
The time to the start of the first moderate or severe fatigue = date of onset of the first moderate or severe fatigue – date of first dose of IP + 1.  
Patients who never reported a moderate or severe AE of fatigue will be censored at the date of last contact.
- Time to onset of the first severe treatment-emergent fatigue  
The time to the start of the first severe fatigue will be calculated by date of onset of the first severe fatigue – date of first dose of IP + 1.  
Patients who never reported a severe AE of fatigue will be censored at the data of last contact.

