### Last Dose Date

Last dose date is defined as day of the last dose of IP. For subjects ongoing at time of analysis, last dose date will be considered the date of the most recent study visit in the database for that subject.

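### The three nested time-to-pruritus analyses use two different censoring dates, one of them undefined, so their Kaplan-Meier curves can rest on different risk sets

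*SAP*

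**What the plan says.** SAP section 10.3.5 plans three time-to-event analyses of treatment-emergent pruritus, each nested in the one before. Their censoring rules are:

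- Any severity: "Patients who never reported an AE of pruritus will be censored at the date of last contact".
- Moderate or severe: "Patients who never reported a moderate or severe AE of pruritus will be censored at the date of completion or discontinuation".
- Severe: "Patients who never reported a severe AE of pruritus will be censored at the date of completion or discontinuation".

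All three are reported in the same way, with quartiles, confidence intervals and percentage censored, and "KM estimates will be plotted as a “survival curve” for each treatment group".

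Elsewhere the SAP uses one date. All three fatigue analyses in 10.3.6 are censored at last contact; for the middle one, "Patients who never reported a moderate or severe AE of fatigue will be censored at the date of last contact". Section 9.6 says of the clinical outcome events that "subjects who do not experience an event will be censored at the time of their last contact".

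Section 10.3.1 sets the window for a new-onset treatment-emergent event: "An AE starting on or after the first study drug dose and within 30 days after the last dose of study drug". Section 5 tabulates completion of and withdrawal from study treatment separately from completion of and withdrawal from the study.

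**The concern.** Nested endpoints are easiest to read when they share one follow-up period, because differences between the curves then reflect severity. Here the first curve can follow a patient to last contact while the other two drop the same patient earlier. No reason is given. The parallel fatigue text suggests a drafting slip rather than a choice.

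The second date is also open to two readings. Because section 5 keeps treatment and study status apart, two programmers could each follow 10.3.5 faithfully and produce different curves from the same data.

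Safety and tolerability is part of the primary objective (2.1.1), and 10.3.5 presents these analyses as its way to explore how pruritus relates to the investigational product. If early stopping differs between arms, any distortion can differ between arms too.

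**Working it through.** The SAP gives no figure for these analyses, so there is none to reproduce. The check applies the written rules to a small example.

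**Inputs from the SAP.** About 50 patients randomized 1:1 (3.3), so about 25 per arm. The only planning rate for stopping is 15%, given for the PK sample size (3.3): 0.15 × 25 = 3.75, or about 4 patients.

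**Assumptions.** Four patients without pruritus stop drug on day 90 and stay in contact beyond day 200. One patient has a first-ever pruritus event on day 200, and it is severe. The other 20 are still on treatment on day 200.

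**Formula.** With a single event, the Kaplan-Meier estimate after it is 1 − S = d/n, where d = 1 and n is the number at risk just before the event.

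| Censoring rule | Any pruritus | Severe pruritus |
|---|---|---|
| As written, discontinuation = stopping drug | 1/25 = 4.0% | 1/(25 − 4) = 1/21 = 4.8% |
| As written, the two dates coincide | equal | equal |
| Last contact for both | 1/25 = 4.0% | 1/25 = 4.0% |
| Earlier of last contact and last dose + 30 days | 1/21 = 4.8% | 1/21 = 4.8% |

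In the last row the four early stoppers are censored on day 90 + 30 = day 120, before the event.

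The same event enters both columns, so the 0.8-point gap in the first row comes only from the censoring dates. If discontinuation means leaving the study, a gap needs contact to continue after study exit. If last contact falls before the recorded completion or discontinuation date, the severe risk set is enlarged instead and its estimate is too low.

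**Does a common rule guarantee ordered curves?** No. Suppose one patient has mild pruritus on day 10 and severe pruritus on day 500, and 8 of the other 24 are censored on day 100 in both analyses. Any pruritus is 1/25 = 4.0%. Severe pruritus is 1/(25 − 8) = 1/17 = 5.9%.

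A simulation of 4,000 arms of 25 per setting, with all event and follow-up times assumed, points the same way. It counted arms in which the severe curve exceeded the any-severity curve at some time:

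| Gap from completion or discontinuation to last contact | Rules as written | Last contact for all |
|---|---|---|
| 0 days | 12% | 12% |
| 0 to 30 days | 16% | 11% |
| 0 to 90 days | 20% | 9% |
| 0 to 365 days | 35% | 5% |

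Differing dates add crossings, but they are not the only cause.

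**The case against.** The strongest reply is that this is a wording inconsistency in a descriptive output. Section 10 plans no inferential comparison of safety endpoints unless otherwise specified. Within each endpoint both arms follow the same rule, and no formal comparison between severity curves is planned. Pruritus is also covered by incidence tables, new-or-worsened events, event days per patient-year and the VAS. Section 10.3.4 uses the end-of-study date for patient-years, so the study reading is plausible, and under it the gap may be close to zero. All of this stands, and it limits the size of the point. It does not explain two rules for nested endpoints or supply the missing definition.

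Three stronger readings are tempting, and the SAP does not support them.

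- *A severe curve above the any-severity curve is impossible, so seeing one proves the rule wrong.* The mild-then-severe example shows that this can happen under a single rule.
- *Some patients get no time at all.* Read literally, a patient whose only pruritus AE was not treatment-emergent has neither an event nor a censoring rule. But the endpoints are named as treatment-emergent, 10.3.4 restricts AE summaries to such events, and 10.3.5 counts patients without pruritus as censored. That largely settles the intent and leaves a wording mismatch, separate from the dates.
- *Qualifying events after drug stop are lost.* Censoring applies only to patients without the event. A severe event 15 days after the last dose still counts; only the risk set around it is affected.

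It can also be said that last contact throughout is the smaller repair. That is true, and it is an acceptable minimum. Its weakness is that a new-onset event more than 30 days after the last dose cannot be treatment-emergent under 10.3.1, so patients would stay at risk for an event they cannot have.

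**Conclusion.** The inconsistency is real and plain on the page: two censoring dates for three nested pruritus endpoints, one of them undefined, against one date for fatigue and for clinical outcome events. Where the dates differ, the pruritus curves are not comparable with each other.

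The size is modest. With about 4 of 25 patients stopping drug early but staying in contact, the example gives 4.8% against 4.0%. This rests on reading discontinuation as stopping drug, on the assumed event and stopping times, and on borrowing the 15% rate from the PK sample-size section. A reader might infer a larger effect by assuming more early stopping: 10 of 25 would give 1/15 = 6.7%. That is a 40% rate, which the SAP does not support. If the dates coincide, there is no effect.

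Because the analysis is descriptive, the severity is minor. It is still worth correcting before database lock.

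**What to change.** - **One date.** Define one censoring date for the three pruritus analyses and use it for the three fatigue analyses as well. Apply it to every patient without a qualifying treatment-emergent event of the given severity.
- **Preferred date.** The earlier of last contact and last dose of investigational product plus 30 days. This matches the new-onset window in 10.3.1 and the safety period in section 10. It also serves patients still on study, for whom completion or discontinuation has no date, because Appendix A already provides: "For subjects ongoing at time of analysis, last dose date will be considered the date of the most recent study visit".
- **Worsening events.** Section 10.3.1 sets no 30-day limit on worsening of an AE that began before the first dose. For these analyses, hold such events to the same window; otherwise an event could fall after censoring.
- **Minimum alternative.** Use last contact for all three pruritus analyses, as 10.3.6 does for fatigue.
- **Wording.** Describe censored patients in all six analyses as those without a treatment-emergent event of the stated type and severity, rather than those who never reported such an AE.

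The cost is a few lines of SAP text and one derived variable. The preferred date shortens follow-up in the curves. Neither option ensures ordered curves in arms of about 25, and the SAP should not suggest that it does.

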### **10.3.6. Fatigue Adverse Events**

Fatigue: Treatment-emergent fatigue is defined as any PT which includes “Fatigue.” New or worsened treatment-emergent fatigue is defined as follows:

- Any mild, moderate, or severe treatment-emergent fatigue events in patients with no fatigue at baseline, or
- Worsening of the severity of the baseline condition in patients with fatigue at baseline.

Baseline fatigue is defined as the Investigator’s rating of severity as collected on the PBC Disease History eCRF. Patients whose baseline severity is severe will be counted as worsening if an AE of fatigue with severe is recorded.

An analysis of treatment-emergent fatigue event days per patient years on study will be performed. The days at each severity grade, including the total days of event, the total patient

years on study, and the event days per patient year on study at each severity grade, including the total, will be summarized.

In order to explore the relationship between fatigue and the IP, the following time-to-event analyses will be performed:

- Time to first onset of treatment-emergent fatigue  
The time to the start of the first episode = date of onset of first episode – date of first dose of IP + 1.  
Patients who never reported an AE of fatigue will be censored at the date of last contact.
- Time to onset of the first moderate or severe treatment-emergent fatigue  
The time to the start of the first moderate or severe fatigue = date of onset of the first moderate or severe fatigue – date of first dose of IP + 1.  
Patients who never reported a moderate or severe AE of fatigue will be censored at the date of last contact.
- Time to onset of the first severe treatment-emergent fatigue  
The time to the start of the first severe fatigue will be calculated by date of onset of the first severe fatigue – date of first dose of IP + 1.  
Patients who never reported a severe AE of fatigue will be censored at the data of last contact.

The analysis of time to first onset of treatment-emergent fatigue AE, time to onset of the first moderate or severe treatment-emergent fatigue, and onset of the first severe treatment-emergent fatigue will include the number of patients with fatigue (first onset, first moderate or severe, first severe), the number of patients without fatigue (censored), and the minimum and maximum times in days. KM estimates will be calculated by treatment group. The quartiles, including the median time-to-event and their corresponding 2-sided 95% CIs, will be presented. KM estimates will be plotted as a “survival curve” for each treatment group.

## **10.4. Clinical Laboratory Evaluations**

Laboratory parameters will be summarized in standard international (SI) system of units by treatment group. Re-test or unscheduled results will not be summarized but will be included in the data listings. Baseline is defined as the mean of all available evaluations prior to treatment. All clinical laboratory data will be listed by subject and visit.

### **10.4.1. Hematology**

Descriptive statistics will be used to summarize the results and change from Baseline to each on-study evaluation visit for hemoglobin, hematocrit, white blood count with differential, neutrophils, lymphocytes, monocytes, eosinophils, basophils, platelets, red blood cell count (including MCV, MCH, MCHC).

In addition, shift tables (ie, low-normal-high at baseline versus low-normal-high at post baseline visit in a 3-by-3 contingency table) from baseline to worst value, last value, and at each scheduled post-baseline visit will be provided for hematology and serum chemistry by treatment group to assess changes in laboratory values from baseline to each on-study evaluation.

Quantitative laboratory tests containing less than (<) and greater than (>) symbols are test results that are below and above quantifiable limits, respectively. In order to retain these values for analysis purpose, the following imputations will be done within the analysis datasets:

- For laboratory test results that are below the quantifiable limit:
  - Imputed laboratory results = (numeric portion of the result) x 0.9.
- For laboratory test results that are above the quantifiable limit:
  - Imputed laboratory results = (numeric portion of the result) x 1.1.

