### 9.1. MELD Score

MELD score is derived from the patient's serum total bilirubin, serum creatinine, and INR, as appropriate, to predict survival ([Kamath 2007](#)). MELD score will be calculated and reported for visits where these parameters are measured as described in the protocol. An increasing MELD score is associated with increased severity of hepatic dysfunction and increased 3-month mortality risk.

- Summary statistics of MELD score including baseline values, change from baseline, and Percentage change from baseline values will be presented by treatment group and by each scheduled post-baseline visit.
- Analysis of change from baseline in MELD score will be analyzed using the Wilcoxon Rank Sum Test. The tabulation will include median, interquartile range for each treatment group, median differences and 95% CI of the median differences between treatment groups using the Hodges-Lehmann estimate. If the median differences between treatments are not symmetrical around the median, the Sign Test may be used.
- MELD score will be presented in shift tables showing the shift from baseline to each scheduled post-baseline visit by the count and percentage of patients within each shift classification (<10, 10 to <12, 12 to <13, 13 to <14, 14 to <15, and  $\geq 15$ ).

The MELD Score analyses will be repeated for MELD-Na

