#### **10.4.3. Coagulation**

Descriptive statistics will be used to summarize the results and change from Baseline to each on-study evaluation visit for PT, PTT, INR.

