#### **10.6. Electrocardiogram (ECG)**

The central read ECG data will be analyzed based on methodology recommended in the International Conference on Harmonisation (ICH) E14 guideline, The Clinical Evaluation of QT/QTc Interval Prolongation and Proarrhythmic Potential for Nonantiarrhythmic Drugs.

Overall interpretation results for ECGs and the investigator interpretation results are collected as normal, abnormal not clinically significant (NCS), and abnormal clinically significant (CS). Subjects whose interpretations shift from normal to abnormal (CS or NCS) will be listed separately, including description of the abnormality and any associated comments.

ECG data will be listed by subject and visit.

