### Baseline and Change from Baseline

The baseline value for statistical analyses of quantitative parameters is defined as the mean of all available evaluations prior to the first administration of IP, unless otherwise specified. Values collected at unscheduled visits prior to the start of the IP administration will be included in the calculation of baseline values. If there is only one evaluation prior to the first administration of IP then the available data from this evaluation will be used as the baseline value.

The baseline value for analyses of lipid parameters is defined as the last fasted evaluation prior to the first administration of IP.

The baseline value for analyses of qualitative parameters (eg, normal/abnormal) is defined as the last evaluation prior to the first administration of IP.

Baseline values defined above will not change regardless if a subject stops taking IP and begins taking commercially marketed OCA.

Change from baseline = (post-baseline value – baseline value).

Percent change from baseline =  $100 * (\text{post-baseline value} - \text{baseline value}) / \text{baseline value}$

For the purpose of tabulations, the unscheduled post-baseline values generally will be excluded from summary tables, but will be included in data listings. Unscheduled visits will be considered for analyses of shift from baseline to worst value (low-normal-high).

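### The low-normal-high laboratory shifts, the open MELD band at 15 and the ECG listing cannot show further worsening from an already abnormal baseline, and INR has no shift table

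*SAP*

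**What the plan says.** **Laboratory shifts (SAP 10.4.1).** The plan calls for "shift tables (ie, low-normal-high at baseline versus low-normal-high at post baseline visit in a 3-by-3 contingency table", from baseline to the worst value, the last value and each scheduled visit. These "will be provided for hematology and serum chemistry by treatment group". No severity grades and no multiples of the upper limit or of baseline are used.

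**INR (SAP 10.4.3).** Coagulation is a separate heading: "Descriptive statistics will be used to summarize the results and change from Baseline to each on-study evaluation visit for PT, PTT, INR". No shift table is named there.

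**MELD (SAP 9.1).** "MELD score will be presented in shift tables showing the shift from baseline to each scheduled post-baseline visit". The bands are "<10, 10 to <12, 12 to <13, 13 to <14, 14 to <15", then an open band of 15 and above. The same analyses are repeated for MELD-Na.

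**ECG (SAP 10.6).** "Subjects whose interpretations shift from normal to abnormal (CS or NCS) will be listed separately". All ECG data are also listed by subject and visit.

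**Unscheduled results.** Section 10.4 says: "Re-test or unscheduled results will not be summarized but will be included in the data listings". Appendix A, Baseline and Change from Baseline, says: "Unscheduled visits will be considered for analyses of shift from baseline to worst value (low-normal-high".

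**The concern.** Safety and tolerability are part of the primary objective (SAP 2.1.1), and patients are enrolled because their liver function is already impaired (SAP 3.1). The harm of interest is often an abnormal value that becomes more abnormal. A display that classifies a value only as low, normal or high, or that ends in an open top class, puts such a patient in the same cell before and after.

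At stake is whether a reader of the study report can see, by arm, how many patients deteriorated from their own starting point. With about 25 patients per arm, such a count is the natural way to show a few serious excursions. It would otherwise have to be pieced together from listings.

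**Working it through.** There is no stated figure to reproduce: the section is descriptive and the SAP tests no formal hypothesis (2.2). The check applies the SAP's own classification rules to example values.

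**1. Laboratory 3-by-3 table.** The SAP gives no reference range, so a bilirubin upper limit of 1.2 mg/dL is assumed for illustration.

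| Baseline (mg/dL) | Post-baseline (mg/dL) | Cell | Change shown? |
|---|---|---|---|
| 0.9 | 2.5 | normal to high | yes |
| 1.5 | 3 | high to high | no |
| 2.5 | 5 | high to high | no |
| 4 | 12 | high to high | no |
| 2.5 | 1.0 | high to normal | yes (improvement) |

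The high-to-high result does not depend on 1.2; it holds for any upper limit below the baseline value. Taking the worst value changes nothing, because a worse high value is still high. The mirror case is a low albumin or platelet count that falls further.

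**2. MELD bands.** Integer baselines from 6 to 24 were classified before and after a rise.
- A rise of 3 changes band from every baseline of 7 to 14.
- A rise of 5 changes band from every baseline of 6 to 14.
- A rise of 1 changes band from 9 and from 11 to 14, but not from 10.
- From 15 upward no rise changes band; 15 to 25 stays in the top class.

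**3. ECG.** There are three interpretation classes: normal, abnormal not clinically significant (NCS), abnormal clinically significant (CS). The separate listing is triggered by normal to NCS and normal to CS. The third possible worsening, NCS to CS, does not trigger it.

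**4. How many patients start abnormal (SAP Table 2).** Class C needs at least 10 points.
- Maximum without any laboratory factor above 1 point: ascites 3 + encephalopathy 3 + bilirubin 1 + albumin 1 + prothrombin time/INR 1 = 9, which is below 10.
- So every class C patient has at least one of the three laboratory factors above 1 point. At 20% of 50, that is at least 10 patients, or about 10/2 = 5 per arm under stratified 1:1 randomization.
- Class B (7 to 9 points) can arise from 90 point combinations. In 6 of them all three laboratory factors score 1, leaving 90 - 6 = 84 with at least one above 1. These are combinations, not patient frequencies.

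**5. Is the gap closed by a planned count elsewhere?**
- Section 10.3.3 makes a persistent 3-point MELD rise from baseline an adverse event of special interest. The summary tables and listings in 10.3.4 include none for events of special interest.
- The time-to-MELD-15 event in 9.6 applies only to baseline MELD of 12 or less, so patients entering at 15 or more are outside it.
- The Child-Pugh component counts in 9.2 are marginal counts per visit, not within-patient changes. Their worst categories are open (bilirubin above 3.0 mg/dL, albumin below 2.8 g/dL, INR above 2.3).
- Unscheduled peaks can enter only the worst-value low-normal-high table, which cannot show them when baseline is already out of range in that direction.

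**The case against.** The strongest reply is that the SAP plans much more than shift tables, and most of that reply stands.

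- **MELD.** A reader might infer that MELD worsening cannot appear at all. It can: the bands are absolute scores, and most rises below 15 change cell. Only the top band is blind. How many patients enter there depends on eligibility rules in the protocol, which is not at hand.
- **Summaries.** A reader might infer that only means and medians remain, so that a 10-point MELD rise in one of 25 patients shrinks to 10/25 = 0.4. Appendix A requires quartiles, minimum and maximum, so at a scheduled visit that patient appears as a maximum change of at least 10. What the maximum lacks is a patient count by arm, and it excludes unscheduled values.
- **Liver tests and INR.** Section 9.3 analyses change in bilirubin, ALP, ALT, AST, GGT, INR, creatinine, albumin and platelets by ANCOVA and MMRM. Section 9.2 tabulates graded bilirubin, albumin and prothrombin time/INR categories, and a class shift in which B to C shows.
- **Adverse events and listings.** Laboratory worsening reported as an adverse event enters the general TEAE tables, and all laboratory and ECG data are listed. NCS-to-CS changes are therefore in the full ECG listing; they are missing only from the separate extract, which the SAP does not present as a list of every worsening.
- **Not everyone starts abnormal.** Some class B patients can have all three laboratory factors at 1 point, and section 6 defines a Rotterdam low group with normal bilirubin and albumin. The 3-by-3 table also shows returns to normal.
- **Unscheduled results.** Appendix A can be read as a specific exception to the general rule in 10.4. That is reasonable, but 10.4 has no cross-reference and the exception does not mention re-tests.

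None of this supplies a count by arm of patients who worsen from an already abnormal value.

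**Conclusion.** The point holds in a limited form. The 3-by-3 laboratory tables, the MELD band of 15 and above, and the separate ECG listing cannot show further worsening from an already abnormal baseline, and INR has no shift table. Other outputs give partial coverage. No planned laboratory, MELD or ECG table counts such patients by arm, and the SAP's own 3-point MELD criterion has no dedicated output.

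The affected group includes every Child-Pugh C patient on at least one test (at least 10 of about 50), and possibly many but not all Child-Pugh B patients. This assumes that a Table 2 score above 1 point also lies outside the laboratory's reference range. The SAP gives no ranges, and an albumin just under 3.5 g/dL could be an exception. If the only raised factor is INR, the chemistry tables are unaffected for that patient, but INR has no shift table to show its worsening.

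This is a shortfall in how safety is displayed. It does not invalidate any planned analysis, and low-normal-high shifts are not wrong in themselves. It is worth correcting because it concerns a primary objective and the data are already collected.

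**What to change.** 1. In 10.4, supplement the 3-by-3 tables with counts by arm of the worst post-baseline value relative to the patient's own baseline. For ALT, AST, ALP, total and direct bilirubin, INR and creatinine use, for example, at least 1.5, 2, 3 and 5 times baseline; for albumin use falls of fixed size.
2. In 9.1, split the top MELD band (for example 15 to <20, 20 to <25, 25 and above) and tabulate by arm the patients with a rise of 3 points or more, the threshold already in 10.3.3. Do the same for MELD-Na.
3. In 10.6, add changes from abnormal NCS to abnormal CS to the separate listing.
4. Reconcile 10.4 with Appendix A by stating in both places that unscheduled and re-test results count toward the worst value.

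The cost is SAP wording and a few extra tables before database lock, from data already held. The downside is that categories relative to baseline will flag some ordinary fluctuation where the baseline is near normal.
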